• Diarrhea: Diarrhea should be treated promptly with appropriate supportive care, including administration of an anti-diarrheal agent according to standard practice guidelines. Anti-diarrheal agents should not be taken prophylactically. Patients should be instructed to begin taking anti-diarrheal medication at the first sign of: 1) poorly formed or loose stool, 2) occurrence of more bowel movements than usual in one day or 3) unusually high volume of stool. Anti-diarrheal agents should be deferred if blood or mucus is present in the stool or if diarrhea is accompanied by fever. In this setting, appropriate diagnostic microbiologic specimens should be obtained to exclude an infectious etiology. Patients should also be advised to drink liberal quantities of clear fluids to help prevent dehydration. Octreotide can also be considered to aid with management of diarrhea. If diarrhea is severe (ie. requiring IV hydration) and/or associated with fever or grade 3 or 4 neutropenia, broad spectrum

antibiotics should be considered. Additionally, hospitalization for IV hydration and eletrolyte correction should be considered.

Patients should be instructed to notify the Investigator or research staff for the occurrence of blood or black stools, symptoms of dehydration, fever, inability to take liquids by mouth, and inability to control diarrhea within 24 hours of using loperamide or other prescribed antidiarrheal medications.

- **Anemia**: Transfusions and/or erythropoietin may be utilized as clinically indicated for the treatment of anemia, but should be clearly noted as concurrent medications.
- **Neutropenia**: Colony-stimulating factors including G-CSF, pegylated G-CSF or GM-CSF according to Institutional Standards.
- **Febrile Neutropenia:** Patients experiencing febrile neutropenia with significant symptoms should be managed in a hospital setting according to standard procedures, with the urgent initiation of IV antibiotic therapy. Patients with febrile neutropenia without symptoms should be managed according to standard guidelines.
- Thrombocytopenia: Transfusion of platelets may be used if clinically indicated.
- Patients requiring radiation or surgery for palliation of a non-target lesion that have not measurably increased in size according to RECIST will be considered to have progressed.
- Participants may receive intravenous fluids on study.
- Bisphosphonates are allowed while on study.

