Please note: aprepitant [Emend] and fosaprepitant are not permitted due to known DDIs.

Patients should be strongly encouraged to maintain liberal oral fluid intake.

Suitable alternative medications may be used, with adequate justification, where the use of any of the above medications might interfere with other study procedures or are deemed insufficient.

^{**}Participants requiring > two dose reductions should discontinue AZD1775

Vomiting	Management/Next Dose for AZD1775
≤ Grade 1	No change in dose
Grade 2	Hold until ≤ Grade 1. Resume at same dose level.
Grade 3	Hold* until < Grade 2. Resume at one dose level lower, if indicated.**
Grade 4	Discontinue treatment and follow for disease progression

^{*}Participants requiring a delay of >3 weeks should discontinue AZD1775.

All patients must receive a 5-HT3 antagonist prior to each dose of AZD1775. Additional doses of 5-HT3 antagonist may be used if needed. In addition, dexamethasone 4 mg PO will be given with each AZD1775 dose as a minimum on the first day of dosing AZD1775 of every 3-5 days dosing period, unless contraindicated or not well-tolerated. Dexamethasone may be continued on further days of dosing, potentially at a lower dose. Dexamethasone or the 5-HT3 antagonist may be given by IV.

Promethazine (Phenergan), prochlorperazine (Compazine), and benzodiazepine may still be used as additional adjunctive treatments during AZD1775 therapy.

Please note: aprepitant [Emend] and fosaprepitant are not permitted due to known DDIs.

Patients should be strongly encouraged to maintain liberal oral fluid intake.

Suitable alternative medications may be used, with adequate justification, where the use of any of the above medications might interfere with other study procedures or are deemed insufficient.

Diarrhea	Management/Next Dose for AZD1775
≤ Grade 1	No change in dose
Grade 2	Hold until ≤ Grade 1. Resume at same dose level.
Grade 3	Hold* until < Grade 2. Resume at one dose level lower, if indicated.**
Grade 4	Discontinue treatment and follow for disease progression
 b	

^{*}Participants requiring a delay of >3 weeks should discontinue AZD1775.

Recommended management: Loperamide antidiarrheal therapy

Dosage schedule: 4 mg at first onset, followed by 2 mg with each loose motion until diarrheafree for 12 hours (maximum dosage: 16 mg/24 hours)

Adjunct anti-diarrheal therapy is permitted and should be recorded when used.

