Participants should be instructed to notify their research doctor for the occurrence of blood or black stools, symptoms of dehydration, fever, inability to take liquids by mouth, and inability to control diarrhea within 24 hours of using loperamide or other prescribed antidiarrheal medications.

If associated with severe (Grade 3 or 4) neutropenia, broad-spectrum antibiotics must be prescribed. Patients should be considered for hospitalization for IV hydration and correction of electrolytes.

^{**}Participants requiring > two dose reductions should discontinue AZD1775.

^{**}Participants requiring > two dose reductions should discontinue AZD1775.

Neutropenia	Management/Next Dose for AZD1775			
≤ Grade 1	No change in dose			
First occurrence	$Hold^*$ until \leq Grade 1. Resume at same dose level.			
Grade 2				
Second or Third	Hold* until \leq Grade 1. Resume at one dose level lower, if indicated**			
Occurrence Grade 2;				
First Occurrence	Hold* until \leq Grade 1. Resume at one dose level lower, if indicated**			
Grade 3 or Second				
Occurrence Grade 3				
Grade 3 Febrile	Hold* until \leq Grade 1. Resume at one dose level lower, if indicated**			
Neutropenia or				
Grade 3 Neutropenia				
with documented				
infection.				
Grade 4 or Second	Hold* until \leq Grade 1. Resume at one dose level lower, if indicated**			
Occurrence Grade 4				
Grade 4 Febrile	Discontinue.			
Neutropenia or				
Grade 4 Neutropenia				
with documented				
infection.				
*Participants requiring	a delay of >3 weeks should discontinue AZD1775.			
**Participants requiring	**Participants requiring > two dose reductions should discontinue AZD1775.			

Note: Consider using G-CSF per institutional standards for neutropenia or febrile neutropenia.

Thrombocytopenia	Management/Next Dose for AZD1775	
≤ Grade 1	No change in dose	
First Occurrence	$Hold^*$ until \leq Grade 1. Resume at same dose level.	
Grade 2		
Second or Third	$Hold^*$ until \leq Grade 1. Resume at one dose level lower, if indicated**	
Occurrence Grade 2		
First Occurrence	$Hold^*$ until \leq Grade 1. Resume at one dose level lower, if indicated**	
Grade 3 or Second		
Occurrence Grade 3		
First or Second	$Hold^*$ until \leq Grade 1. Resume at one dose level lower, if indicated**	
Occurrence Grade 4		
without any evidence		
of bleeding		
Thrombocytopenia	Discontinue.	
haemorrhage (gross		
occult bleeding)		
associated with		
platelet count		
<50,000 uL		

Thrombocytopenia	Management/Next Dose for AZD1775	

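### Sections 5.4 and 6.1 disagree on whether antibiotics are discretionary or mandatory for diarrhea with grade 3 or 4 neutropenia, and 6.1 leaves out 5.4's exception for deferring antidiarrheals

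*Combined protocol and SAP*

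**What the plan says.** Two sections of the protocol give supportive-care instructions for diarrhea.

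**Antibiotics.** In Section 5.4 (Supportive Care, diarrhea bullet), the trigger is diarrhea that is severe and/or "associated with fever or grade 3 or 4 neutropenia, broad spectrum", and the sentence continues after a page break: "antibiotics should be considered". In Section 6.1, below the AZD1775 diarrhea table, the instruction reads: "If associated with severe (Grade 3 or 4) neutropenia, broad-spectrum antibiotics must be prescribed".

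**Antidiarrheals.** Section 5.4 starts them early: "Patients should be instructed to begin taking anti-diarrheal medication at the first sign of: 1) poorly formed or loose stool". It then adds an exception: "Anti-diarrheal agents should be deferred if blood or mucus is present in the stool or if diarrhea is accompanied by fever". In that setting it also asks for microbiologic specimens. Section 6.1 is headed "Recommended management: Loperamide antidiarrheal therapy" and gives the schedule as "4 mg at first onset, followed by 2 mg with each loose motion". It states no exception for fever, blood or mucus. It asks participants to tell their research doctor about fever and about blood or black stools, and 5.4 carries nearly the same notification request.

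**A related rule.** Section 5.4 also has a febrile neutropenia bullet. With significant symptoms, it calls for hospital management and urgent intravenous antibiotics. Without symptoms, it refers to standard guidelines.

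**The concern.** The two sections address the same event and the same treatment with different force. Diarrhea and neutropenia each have their own AZD1775 modification table in Section 6.1, so the protocol expects both, and diarrhea with neutropenia is where the two meet. A clinician working from 5.4 may properly decide against antibiotics. A monitor working from 6.1 would record that decision as a deviation.

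The antidiarrheal text matters for a different reason. Under Section 5.3.1, AZD1775 doses after the first in a cycle can be taken at home, and 5.4 has patients start antidiarrheals themselves. A reader who takes the loperamide schedule from 6.1 alone will not see that 5.4 sets some patients apart. Section 6.1 gives no cue to look elsewhere: it repeats 5.4's notification request almost in full, but not the deferral.

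**Working it through.** No arithmetic applies; the check is a comparison of text. The inputs are the diarrhea bullet and febrile neutropenia bullet in 5.4, and the diarrhea table and the text below it in 6.1.

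**Step 1: is the 5.4 sentence read correctly?** It is split by a page break but reads through without a gap. Its and/or construction makes grade 3 or 4 neutropenia sufficient by itself, so it covers the event named in 6.1.

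**Step 2: is the difference only loose phrasing?** No. The sentence after the 6.1 antibiotic requirement uses the softer verb, consider, for hospitalization. Section 6.1 therefore distinguishes an obligation from a consideration within two sentences.

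**Step 3: compare by situation.**

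| Situation (diarrhea plus) | Antibiotics, 5.4 vs 6.1 | Antidiarrheal, 5.4 vs 6.1 |
|---|---|---|
| (a) Grade 3-4 neutropenia; no fever, blood or mucus | Discretionary vs mandatory: contradiction | Start early in both: no conflict |
| (b) Fever; no grade 3-4 neutropenia | Discretionary vs no rule: no direct conflict | Defer vs start at onset with no exception stated: omission in 6.1 |
| (c) Grade 3-4 neutropenia and fever | Diarrhea texts differ as in (a), but 5.4's febrile neutropenia rule also applies and requires urgent treatment if symptoms are significant | Omission in 6.1, as in (b) |
| (d) Grade 3-4 neutropenia and blood or mucus; no fever | Contradiction, as in (a) | Omission in 6.1, as in (b) |

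**Step 4: does other text settle it?** The febrile neutropenia bullet needs fever, so it does not reach (a) or (d). The neutropenia bullet in 5.4 concerns colony-stimulating factors. The neutropenia table in 6.1 concerns AZD1775 dosing, with a note on G-CSF. The diarrhea row of Table 6-6 concerns cisplatin dosing. None of these assigns a status to antibiotics, and no precedence between 5.4 and 6.1 is stated.

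**Step 5: result.** There is one contradiction, clearest in (a), and one omission, in (b) to (d). They have different triggers: neutropenia for the first; fever, blood or mucus for the second.

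**The case against.** The strongest reply is that the texts can be followed together. Prescribing antibiotics satisfies both sections, since 5.4 permits it and nowhere requires withholding. The requirement in 6.1 can be checked, and meeting it breaches nothing. On antidiarrheals, 5.4 itself begins with early treatment and then carves out an exception, while 6.1 is labelled as recommended management and never says to give loperamide despite fever or blood. A general rule and a specific exception can be read as one, and the notification request in 6.1 brings fever and blood to the doctor's attention. The febrile neutropenia rule covers much of the highest-risk case.

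Most of this stands, and it rules out several stronger readings that a reader might infer:

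- That the sections direct opposite management, or that any course breaches one of them. Only considering and then not prescribing antibiotics, in a patient with grade 3 or 4 neutropenia, departs from 6.1.
- That there are two direct conflicts over one event. The triggers differ, and the antidiarrheal point is an omission.
- That the antibiotic conflict extends to fever alone. Section 6.1 has no antibiotic rule there.
- That 5.4 defers antidiarrheals until infection is excluded. It asks for specimens to exclude an infectious cause, but sets no end-point for the deferral.
- That compliance cannot be monitored. Only the case just described is unclassifiable.

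What the reply does not remove is that case. For diarrhea with neutropenia and no fever, a decision that 5.4 allows is one that 6.1 forbids.

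**Conclusion.** The point holds in limited form. Sections 5.4 and 6.1 contradict each other on the status of broad-spectrum antibiotics for diarrhea with grade 3 or 4 neutropenia. Separately, 6.1's loperamide schedule omits 5.4's deferral for fever, blood or mucus.

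Its size cannot be put in patients. The documents give no rate for diarrhea with grade 3 or 4 neutropenia or with fever. The 25 to 30% figure for myelosuppression under cisplatin in Section 6.2 is not a rate for either combination. Even a known rate would count patients with the event, not patients managed differently because of the wording. The conclusion does not depend on a rate; it rests only on both sections being in force with no stated precedence.

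Objective response, the two-stage rule, the error rates and the analysis population are unaffected. This is a correction to safety wording that should be made because the instruction is contradictory as written. No view is taken here on which clinical rule is right.

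**What to change.** Reconcile the diarrhea text of Sections 5.4 and 6.1 into one instruction, held in one section, with the other referring to it. It should:

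1. give antibiotics in diarrhea with grade 3 or 4 neutropenia a single status, either mandatory or discretionary;
2. state whether 5.4's deferral for fever, or for blood or mucus in the stool, applies to the loperamide schedule in 6.1;
3. state how the diarrhea text relates to the febrile neutropenia rule in 5.4 when both apply.

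Any patient-facing instruction on diarrhea should carry the same text. The clinical content of each item is the sponsor's decision.

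The cost is protocol wording. No procedure, visit or data item is added, and the statistical section needs no change.

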6.2 Dose Delays and Modifications for Cisplatin

Cisplatin will be initially administered at a dosage of 75mg/m² as an IV infusion given every 3 weeks. Patients who experience a Grade 3 or 4 toxicity attributable to cisplatin will have their cisplatin dose reduced to per Table 6-2. Toxicities resulting in myelosuppression, renal insufficiency, ototoxicity, and marked nausea and vomiting are most commonly seen with cisplatin monotherapy. Assessments should be made immediately prior to the scheduled administration of the chemotherapy. If patient needs to discontinue cisplatin therapy, patient can be treated on protocol with AZD1775 monotherapy.

Table 6-2 DOSE MODIFICATION OF CISPLATIN

Dose Level	Cisplatin Dose
0	75mg/m^2
-1	60mg/m^2
-2	50mg/m^2

Dose delays and modifications are summarized in the toxicity table in Table 6-6.

No dose re-escalations are allowed on study, except where noted below.

Expected toxicities for Cisplatin:

Nephrotoxicity

The major dose-limiting toxicity of cisplatin is cumulative nephrotoxicity. Tubular necrosis of both proximal and distal renal tubules has been noted in 28% to 36% of subjects treated with a single dose of 50mg/m^2 . It is first noted during the second week after a dose and is manifested by elevations in BUN and creatinine, serum uric acid and/or a decrease in creatinine clearance. Renal toxicity becomes more prolonged and severe with repeated courses of the drug. Renal function must return to normal before another dose of cisplatin can be given. Nephrotoxicity can be reduced by IV hydration and mannitol diuresis.

Nausea and Vomiting

Cisplatin causes moderate to severe nausea and vomiting in almost all subjects treated. Nausea and vomiting usually begin within 1 to 4 hours after treatment and last up to 24 hours. Various degrees of vomiting, nausea, and/or anorexia may persist for up to 1 week after the treatment. Delayed nausea and vomiting (beginning 24 hours or after chemotherapy) has occurred with complete emetic control on the day of cisplatin therapy. The use of prophylactic and continuing antiemetic medication reduces these adverse effects.

Hypomagnesemia

Hypomagnesemia has been reported in subjects treated with cisplatin and is probably related to renal tubular damage. It may become severe enough to cause tetany. Generally, serum electrolytes return to normal levels when cisplatin is discontinued and supplemental electrolytes are administered.

Ototoxicity

Ototoxicity has been observed in up to 31% of subjects treated with a single dose of cisplatin (50mg/m²) and is manifested by tinnitus and/or hearing loss in the high frequency range (4000 to 8000 Hz). Decreased ability to hear normal conversational tones may occur occasionally. Ototoxicity can be more severe in children than in adults and more frequent and severe with repeated administration. Hearing loss can be unilateral or bilateral and is usually not reversible. During treatment with cisplatin, it is necessary to monitor hearing at each visit as part of a standard physical exam.

Myelosuppression

Myelosuppression occurs in 25 to 30% of subjects treated with cisplatin. The nadirs in circulating platelets and leukocytes occur between days 18 and 23, with most subjects recovering by day 39. Leukopenia and thrombocytopenia are more pronounced at higher doses (>50 mg/m²). Anemia (a decrease in hemoglobin of 2 gm/100ml) occurs at approximately the same frequency and with the same timing as leukopenia and thrombocytopenia.

Neurotoxicity

Cisplatin neurotoxicity is characterized by peripheral neuropathies, which are sensory in nature but can also include motor difficulties such as reduced deep-tendon reflexes and leg weakness. The symptoms usually occur after prolonged therapy (4 to 7 months). Cisplatin therapy should be discontinued when serious neuropathy develops. The neuropathy, however, may progress

further even after discontinuation of treatment.

Hematologic Toxicity

Dose adjustment at the start of a subsequent cycle of therapy will be based on the neutrophil and platelet counts on day 1 of the cycle. ANC must be $\geq 1.0 \times 10^9 / L$ and platelets $\geq 75 \times 10^9 / L$ before the start of each cycle. Treatment should be delayed to allow sufficient time for recovery. Upon recovery, if treatment is resumed, it should be accounting to the guidelines in Table 6-2 with respect to nadir platelet and ANC values for subsequent cycles, except as noted below. A delay in treatment due to hematologic toxicity if more than 3 weeks will result in withdrawal from the study.

The use of colony stimulating factors (filgrastim or pegfilgrastim) is permissible if recommended by the primary treating physician but should be clearly recorded in the medical record and case report form. Prophylactic use of GCSF is not recommended with the first cycle.

If GCSF is initiated, then the required dose modification will be adjusted according to the guidelines in footnote of Table 6-3.

Table 6-3
Dose Adjustments for Cisplatin Based on Hematologic Values for Preceding Cycle

Platelets (×1	0 ⁹ /L)	ANC (×10 ⁹ /L)	Dose of Cisplatin
≥75	and	≥1.0	75mg/m ^{2*}
≥50	or	≥ 0.5	60mg/m ^{2*} ,#
< 50	or	<0.5	50mg/m^{2*} ,@
Recurrence of	grade 3 or 4 th	rombocytopenia after 2 dose reductions	Withdraw subject from study
or			continue on ADZ1775
alone			
Recurrence of	grade 3 or 4 ne	utropenia after 2 dose reductions	Withdraw subject from study
or			
			continue on ADZ1775
alone			

^{*} Treatment should be delayed until recovery of platelets to $\geq 100 \times 10^9 / L$ and ANC to $\geq 1.0 \times 10^9 / L$.

Non-Hematologic Toxicity

For other grade 3 or higher non-hematologic effects (with the exception of grade 3 transaminase elevations and nausea or vomiting), treatment should be delayed until resolution (less than or equal to baseline). Treatment can be resumed at 60mg/m², if deemed appropriate by the treating physician, for all subsequent cycles.

Neurosensory Toxicity

[#] For ANC ≥0.5 treat at 75mg/m² dose if initiating GCSF

[@] For ANC<0.5 treat at 60mg/m² dose if initiating GCSF

Adjustments of the cisplatin dose in subjects with neurosensory toxicity are shown in Table 6-4. Cisplatin therapy should be held for grade 2 or higher neurosensory toxicity and should resume with a dose reduction once it has resolved to grade 1.

Table 6-4
Dose Adjustments for Cisplatin Based on Neurosensory Toxicity

CTCAE Grade	Dose of Cisplatin
0-1	100% of previous dose
2	60mg/m^2
3-4	Withdraw participant from study or continue on AZD1775
alone	

Tinnitus or Significant Hearing Loss

In cases of tinnitus or significant hearing loss, cisplatin therapy should be reduced or stopped, at the discretion of the investigator.

Nephrotoxicity

Cisplatin dose adjustments in subjects with renal toxicity are shown in Table 6-5. Either serum creatinine or estimated creatinine clearance may be used. If a dose delay or dose reduction occurs due to nephrotoxicity, subsequent doses of cisplatin may be escalated based on the renal function on the day of treatment (+/- 3 days) and should be determined based on Table 6-5.

Table 6-5
Cisplatin Dose Adjustments for Renal Toxicity

Creatinine(mg/dl)	OR Creatine Clearance(cc/min)	Dose of Cisplatin
<1.6	>50	75mg/m^2
1.6-2	10-50	60mg/m^2
>2	<10	Delay one week

Other Toxicity

Patients who develop treatment-related grade 3 non-hematological toxicity (except grade 3 transaminase elevations and nausea or vomiting) should have cisplatin therapy delayed until toxicity has resolved to less than or equal to grade 1 or baseline. Cisplatin will be continued at 60mg/m² for subsequent cycles. For grade 3 nausea, vomiting, or transaminase elevation, treatment will be delayed until toxicity resolves to grade 1 or less, and treatment may resume at 75 mg/m² dose. If any toxicity, including those described above, results in a three week treatment delay, patients will be taken off protocol. Patients with grade 4 non-hematological toxicity attributed to cisplatin will come off study unless exception is given by the Protocol Chair. Prior to retreatment, toxicity must resolve to less than or equal to grade 1 or baseline. For ≥ grade 2 Hgb toxicity, at the treating physician's discretion, dose may be reduced by one dose level in addition to transfusions and/or growth factor support as clinically indicated, with the option to re-escalate at physician's discretion. This should be documented in the medical record.

Table 6-6: Cisplatin Toxicity Management and Dose Modification Summary Table

Toxicity Event	Dose Modification	
Hematologic		
$ANC > 1000/mm^3$	None	
$ANC \geq 500/mm^3$	Delay until >1000/mm ³ and reduce to 60mg/m ²	
	(treat at 75mg/mm ² if initiating GCSF)	
$ANC < 500/mm^3$	Delay until >1000/mm ³ and reduce to 50mg/m ²	
	(treat at 60mg/mm ² if initiating GCSF)	
Grade 3 or 4 toxicity	Withdrawal from study or continue	
after 2 dose reduction		
Plt >100,000/mm ³	None	
Plt >50,000/mm ³	Delay until >75,000/mm ³ and reduce to 60mg/m ²	
$Plt < 50,000/mm^3$	Delay until >75,000/mm ³ and reduce to 50mg/m ²	
C 1 2 4	W'.1.11.C	
Grade 3 or 4 toxicity	Withdrawal from study	
after dose reduction		
Gastrointestinal		
Diarrhea		
Grade 3/4 or	Delay until resolution and reduce to 60mg/m ²	
requiring hospitalization		
Vomiting, Nausea		
Grade 3/4	Delay until ≤grade 1 or has returned to baseline and resume at	
	75mg/m ² or with one dose reduction (Per investigator discretion)	
Transaminases		
Grade 3/4	Delay until ≤grade 2 and with one dose reduction	
Neurological		
Neurosensory		
Grade 0-1	None	
Grade 2	Delay until resolves to ≤grade 1 and resume with one dose reduction	
Grade 3-4	Withdrawal from study	
Ototoxicity		
Tinnitus or	Reduce dose or withdraw from study at investigator discretion	
significant hearing loss		
Nephrotoxicity		
Cr <1.6 mg/dl or	None	
CrCl >50 cc/min		
Cr 1.6-2 mg/dl or	50mg/m ²	
CrCl 10-50 cc/min		
Cr>2 mg/dl or	Delay one week	
CrCl <10-cc/min		
Other Toxicity		
Grade 3	Delay until ≤ grade 1 or has returned to baseline and resume at	
	60mg/m^2	
·		

Grade 4	Withdraw from study, unless exception granted by the Principal
	Investigator

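### Section 6.2 gives conflicting cisplatin doses for grade 3 transaminase elevation, and its fixed 60 mg/m² rules fail once a patient has already been reduced

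*Combined protocol and SAP*

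**What the plan says.** The general rule opens Section 6.2: "Patients who experience a Grade 3 or 4 toxicity attributable to cisplatin will have their cisplatin dose reduced to per Table 6-2". Table 6-2 has three levels: 75, 60 and 50 mg/m². The section adds "No dose re-escalations are allowed on study, except where noted below". Two exceptions are then written out: for renal function ("subsequent doses of cisplatin may be escalated based on the renal function on the day of treatment") and for hemoglobin ("with the option to re-escalate at" the physician's discretion).

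The specific rules relevant here are:

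- **Other grade 3 non-hematologic toxicity.** The Non-Hematologic Toxicity paragraph permits resumption at 60 mg/m² "if deemed appropriate by the treating physician, for all subsequent cycles". The Other Toxicity paragraph says "Cisplatin will be continued at 60mg/m² for subsequent cycles". The grade 3 Other Toxicity row of Table 6-6 waits until grade 1 or less "or has returned to baseline and resume at" 60.
- **Diarrhea, grade 3/4 or leading to admission.** Table 6-6: "Delay until resolution and reduce to" 60 mg/m².
- **Grade 3 transaminase elevation.** Both text paragraphs exempt it from the 60 mg/m² rule. The Other Toxicity text then waits for grade 1 or less and allows 75. Table 6-6 waits for grade 2 or less and requires one dose reduction. Section 5.2.2 also uses grade 2 or less for starting a later cycle.
- **Grade 2 neurosensory toxicity.** The cell in Table 6-4 says 60. The text above that table calls for a dose reduction, and Table 6-6 for one dose reduction.

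**The concern.** A dose-modification section has to give one dose for one event in one patient. Here the transaminase rule gives two answers for a patient at full dose on a first event. The fixed 60 mg/m² rules are written as if every patient were still at 75. Read literally for a patient already at 60, they repeat the dose at which the grade 3 event occurred.

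The earlier reduction need not have been for the same toxicity. A patient can already be at 60 because of blood counts (Table 6-3) or grade 2 neurosensory toxicity (Table 6-4), so the problem can arise at a first grade 3 diarrhea. At stake are patient safety and uniform cisplatin exposure across investigators.

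**Working it through.** No sample size, power or error-rate figure is involved. The check applies each rule at each possible current dose.

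**Inputs.** Table 6-2 levels (75, 60, 50); the general grade 3–4 rule and the re-escalation ban (opening of Section 6.2); the fixed 60 (Non-Hematologic Toxicity and Other Toxicity text; Table 6-6). Relative change = new dose / current dose − 1.

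**1. Grade 3 transaminase elevation, first event at 75**

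| Source | Recovery needed | Next dose | Change |
|---|---|---|---|
| Other Toxicity text | grade 1 or less | 75 allowed | 75/75 − 1 = 0% |
| Table 6-6 | grade 2 or less | 60 (one reduction) | 60/75 − 1 = −20.0% |

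The gap is 75 − 60 = 15 mg/m², and the recovery thresholds differ as well. The table's dose fits the general grade 3–4 rule if the event is attributed to cisplatin, and its threshold matches Section 5.2.2.

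**2. Other grade 3 non-hematologic toxicity, or grade 3 diarrhea**

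| Current dose | General rule with Table 6-2 | Fixed rule | Result |
|---|---|---|---|
| 75 | 60 (60/75 − 1 = −20.0%) | 60 (−20.0%) | agree |
| 60 | 50 (50/60 − 1 = −16.7%) | 60 (60/60 − 1 = 0%) | gap of 60 − 50 = 10 mg/m² |
| 50 | no lower level | 60 (60/50 − 1 = +20.0%) | a re-escalation, not among the written exceptions |

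For diarrhea below grade 3 that leads to admission, the general grade 3–4 rule does not apply. An instruction to reduce to 60 still cannot be carried out at 60.

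At 50, stopping cisplatin is open: Section 6.2 lets a patient who must discontinue cisplatin stay on protocol with AZD1775 alone. It is not stated as the rule for this event.

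**3. Grade 2 neurosensory toxicity**

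At 75, the Table 6-4 cell and one dose reduction both give 60. At 60, the cell gives 60, while the text above it and Table 6-6 require a reduction, to 50. At 50, the cell names a higher dose. The general grade 3–4 rule plays no part here because the event is grade 2; the defect lies in that one cell.

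**4. Related points that the repair must cover**

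- For creatinine 1.6–2 mg/dl or clearance 10–50 cc/min, Table 6-5 gives 60 and Table 6-6 gives 50, a gap of 10 mg/m². Renal function is therefore not a settled route to 60.
- The Table 6-3 footnotes name 75 (ANC at least 0.5) or 60 (ANC below 0.5) when G-CSF is started. The section does not say whether these count as exceptions to the re-escalation ban.
- The AZD1775 table for other non-hematologic toxicities in Section 6.1 steps down from the current level, so it avoids the problem.

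**The case against.** The best defense is that the general sentence is defective (a word is missing before the table reference) and never says one level below the current dose. The 60 mg/m² is level −1, so it reads naturally as the first-event dose from 75, where there is no conflict. On that view the plan leaves a repeat-event rule unstated and does not contradict itself. This has some force for the fixed-60 rules. But the sentence does require a reduction, 50 is the only level below 60, and the Other Toxicity text says without condition that treatment continues at 60. Nothing says which governs. The defense does not touch the transaminase conflict, which arises at 75.

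A second argument is that discretion covers the gap. AZD1775 starts in cycle 2, so a patient already at 60 is normally in combination therapy. There, Section 6.1 recommends modifying AZD1775 first and makes a second reduction a joint decision of the treating physician and the Principal Investigator. Section 5.5 ends treatment for unacceptable adverse events, and Section 6.2 takes patients off protocol after a three-week delay. These safeguards stand and narrow the exposure. None names the cisplatin dose. The clearest gap in the joint decision is a patient continuing on cisplatin alone.

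A reader might infer that a patient at 50 has no permitted course, or that no non-hematologic toxicity has a stopping rule. The documents support neither: AZD1775 alone is available, and grade 3–4 neurosensory toxicity ends cisplatin in Tables 6-4 and 6-6.

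**Conclusion.** Section 6.2 contains conflicting cisplatin rules that should be corrected. The clearest is grade 3 transaminase elevation: 75 against 60 mg/m² at a first event, with different recovery thresholds. The fixed 60 for other grade 3 toxicity and diarrhea is sound from 75, gives no reduction at 60 (10 mg/m² above the next level), and at 50 names a dose that the ban excludes. The grade 2 neurosensory cell of Table 6-4 disagrees with its own text and with Table 6-6 once the patient is below 75.

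This rests on reading the general sentence as a step down Table 6-2 and on the renal and hemoglobin provisions being the only clearly written re-escalation exceptions. The documents give no basis for estimating how many patients would be affected. A reader might take the conflict as a threat to the trial's conclusions on response; the documents do not support that, since the two-stage design's sample size and error rates do not depend on these rules. Grade 4 non-hematologic toxicity is outside this point.

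**What to change.** In a protocol amendment:

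1. Reword the fixed-60 rules (Non-Hematologic Toxicity and Other Toxicity text; diarrhea and grade 3 Other Toxicity rows of Table 6-6) and the grade 2 cell of Table 6-4 as: one Table 6-2 level below the current dose; if already at 50 mg/m², stop cisplatin (AZD1775 alone or off treatment).
2. Give one transaminase rule in both text and table. The default should be Table 6-6 (grade 2 or less, one dose reduction), because it matches Section 5.2.2 and the general rule. Both text paragraphs deliberately exempt transaminases from the 60 mg/m² rule, so the sponsor should confirm which was intended.
3. Reconcile Table 6-5 (60) with Table 6-6 (50) for creatinine 1.6–2 or clearance 10–50.
4. List the re-escalation exceptions explicitly: renal, hemoglobin, and whether the Table 6-3 G-CSF footnotes count. A blanket statement that no named dose may exceed the current one would override those footnotes without discussion.

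The cost is a few reworded sentences and table cells. No patients, visits or tests are added.
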